Step 3. Registration: After manual boundary detection, the CASCADE Program will automatically identify and outline the lumen and wall boundary of the carotid artery in the remaining 4 sequences. An example is shown in Figure 3 below. Expert readers will review the outlines generated by CASCADE, and have the opportunity to manually override errors in the automated outlines that may occur as a result of marginal image quality or flow artifact.

Step 4. Auto-segmentation: The CASCADE Program will automatically identify and quantify the tissue component within the arterial wall. Expert readers will then review the output of CASCADE to insure correct classification of the plaque components. An example is shown in Figure 4 below with loose matrix in purple and lipid content in yellow.

The image analysis for this study will be performed at the time of completing both MRI examinations. By doing so, a region of each carotid artery, covered by both baseline and 2-year scans, will be identified and image analysis will be performed within the region. This will allow the same reviewers to analyze all images and therefore to reduce the inter-reader variability. The analysis will be performed at Vascular Imaging Lab using CASCADE with automated tissue segmentation capability using MEPPS.

(c) Plaque Tissue Composition: This will be calculated based on each identified tissue volume and wall volume at each given location: tissue volume/wall volume x (100%), and presented as percentage.

(d) Summary of Plaque Variables: CASCADE can produce a list of comprehensive plaque assessments. Plaque burden measurements will include the carotid lumen, wall, and outer-wall area in mm², wall thickness in mm, and wall/outer-wall ratio (a normalized wall index that is adjusted for carotid artery size difference) that is equivalent to the % of atheroma area used in the coronary intravascular studies. The plaque tissue characteristics will be presented as absolute measurement in mm² and as a proportion of the corresponding vessel wall area, expressed as in % lipid, % loose matrix, % calcium, % fibrous tissue and % hemorrhage. Additionally, the plaque integrity will also be evaluated and described as ruptured, thin or thick fibrous cap, with and without ulceration, with and without thrombus.

[figure not shown]

Ultrasound Examination:

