carried out by using time-varying covariates. For the analysis of CV risk in relation to plaque “velocity”, (ii), the methodology is the same, except that each person will have only one interval, from the 3-year MRI scan onward. Independent variables will be the rate of change of plaque characteristics during the first 3 years (e.g., annual % change in lipid composition), as well as the value of plaque variables at the 3-year point, a new “baseline”. For both the baseline and velocity part of these analyses we will attempt to build a multivariate model(s) that will allow us to characterize the CV risk for a given patient. These models will use not only the MRI variables but currently identified risk factors as well, such as age and gender. Our modeling will also address an important issue: Do the plaque variables, even if statistically significant, really add to the prediction of cardiovascular risk? In other words, are the plaque variables really adding something independent of what is already known about risk? We can address this issue by comparing a Cox proportional hazards model with traditional risk factors only, such as age, gender, and smoking status, to a model that includes these traditional factors and also includes any important plaque variables that have detected. We can use either the change in a pseudo-R² statistic (based on likelihood) or use logistic regression and note the increase in the area under the ROC curve when the plaque variables are added into the model with the traditional risk factors. This comment applies to any analyses where there are traditional (known) risk factors available. While statistical significance of a plaque variable may help us to understand the biology better, it is also helpful to know if the use of plaque variables notably increases the prediction of CV events for individuals.

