5. Correlation among baseline plaque, plaque changes and laboratory variables: This set of analyses deal with correlation between baseline plaque characteristics and plaque progression or between laboratory measurements, such as lipids and inflammatory markers, and plaque composition and progression. The simplest form of these analyses will be the Pearson or Spearman correlation (and scatterplots) between pairs of variables, such as the change over two years in plaque lipid composition vs. the corresponding change in HDL-C concentration. The correlations will be based on a pair of variables, one each selected from these separate sets of variables: (a) baseline plaque variables, (b) baseline laboratory measurements, (c) rate of change of plaque variables over time, (d) rate of change of laboratory measurements over time. Each different pair of variables and their correlation test a hypothesis of interest. For example, selection of the change in plaque over time and change in a laboratory variable over time tests the hypothesis that these items progress or regress in parallel. These analyses are readily expanded to include covariates in multivariate models. For example, if baseline HDL-C and baseline plaque lipid composition are both related to progression, we would want to try including them as independent variables in a model for progression in order to tease out the independent effect of each of the two variables.

The study will be able to detect even rather weak correlations. With our sample size of at least 180 patients who have complete data for up to 3 years we will be very likely to detect a true correlation of $r = \pm 0.18$ or larger between variables of interest. We are assuming 80% power, 2-sided test, $p < 0.05$.

Drs. [name], [name], [name] at the University of Washington, and [name] (biostatistician at Mountain-Whisper-Light Statistics) developed the statistical analysis

plan. Analyses will be carried out in SAS, STATA, R and SPSS and performed by the Mountain-Whisper-Light Statistics.

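### F.3.5 allows a baseline variable to be tested against its own change with r = 0 as the null; shared baseline error makes that null wrong, by an amount the documents do not let us judge

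*Combined protocol and SAP*

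**What the plan says.** Section F.3.5 opens: "This set of analyses deal with correlation between baseline plaque characteristics and plaque progression". It draws each pair of variables from separate sets, the first three listed as "a) baseline plaque variables, (b) baseline laboratory measurements, (c) rate of change of plaque variables over time". The fourth is rate of change of laboratory measurements. On method it says: "The simplest form of these analyses will be the Pearson or Spearman correlation". On status it says: "Each different pair of variables and their correlation test a hypothesis of interest". The power statement that closes the section uses a two-sided test at p < 0.05 with at least 180 complete patients. No null other than zero correlation is given.

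Nothing bars pairing a variable with its own change. The section's multivariable example puts baseline plaque lipid composition into a model for progression.

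F.3.3 is related. It evaluates the baseline value of the outcome in the regression for 3-year change. It also says that a treatment-by-baseline interaction would naturally be tested if both main effects are important and statistically significant.

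**The concern.** Change is measured from the baseline scan, so the baseline error sits in both members of an own-change pair, with opposite signs. The ordinary correlation test then asks whether r differs from zero when, with no true relation, it is already expected to be below zero. A result such as plaques with more lipid at baseline regressing more could be partly or wholly regression to the mean, yet be reported as biology.

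The same structure arises in three other places:

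- Plaque pairs that share baseline scan error. Percent tissue is defined in D.3 as "tissue volume/wall volume x (100%), and presented as percentage", so percent lipid and wall volume share a term; the direction of bias there is not known.
- A laboratory variable paired with its own change, such as baseline HDL-C with HDL-C change.
- The baseline main effect on change in F.3.3, when it is interpreted or used to trigger an interaction test.

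It does not arise when a plaque variable is paired with a laboratory variable, because the two carry separate measurement errors.

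**Working it through.** **Inputs from the documents.** n = 180 and a two-sided 5% level (F.3.5); four annual scans (A.2).

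**Inputs not in the documents, so assumed.** R is reliability counting scan-specific error only. c is the variance of true 3-year change divided by the variance of true baseline. D.3 claims accuracy similar to expert review without a figure, and the ultrasound section plans observer variability for CIMT only. Averaging over slices, imaging both arteries and using the same readers should raise R by an unknown amount.

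**The plan's own figure.** F.3.5 says r = ±0.18 is detectable with 80% power at n = 180. By Fisher's z the two-sided power is 68%; 80% needs 240 patients. That is a separate matter, and nothing below depends on it.

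**Formula, two scans.** Set true baseline variance to 1 and error variance to e = (1 − R)/R. Observed baseline is T + E0 and observed change is D + E3 − E0. If D is independent of T and the errors are independent, the covariance is −e, the variances are 1 + e and c + 2e, and

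r = −e / √[(1 + e)(c + 2e)].

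**Formula, four-scan slope, linear true change.** Scaled to three years, the weights on the scans are −0.9, −0.3, 0.3 and 0.9. Their squares sum to 1.8, so

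r = −0.9e / √[(1 + e)(c + 1.8e)].

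**Rejection rate.** With m = atanh(|r|) × √177, the rate is Φ(m − 1.96) + Φ(−m − 1.96).

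**One case in full.** R = 0.90, c = 0.25: e = 0.1111; r = −0.1111 / √(1.1111 × 0.4722) = −0.153; m = 2.057; rejection = 54%.

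| R | c | r, 0 to 3 years | False significance | r, four-scan slope | False significance |
|---|---|---|---|---|---|
| 0.90 | 0.25 | −0.153 | 54% | −0.141 | 47% |
| 0.90 | 1 | −0.095 | 25% | −0.087 | 21% |
| 0.95 | 0.25 | −0.086 | 21% | −0.079 | 18% |
| 0.95 | 1 | −0.049 | 10% | −0.044 | 9% |
| 0.97 | 0.25 | −0.054 | 11% | −0.050 | 10% |
| 0.97 | 1 | −0.030 | 7% | −0.027 | 6% |

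Simulation of the two-scan case (20,000 trials) agrees. At R = 0.90, Pearson rejects 54.9% (c = 0.25) and 24.5% (c = 1), and Spearman 50.9% and 22.8%. With no error (R = 1) both reject about 5%. Choosing Spearman therefore does not remove the problem.

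These ranges are not bounds. Letting c run from 0 to 2.25 widens the two-scan range to about 14-86% at R = 0.90 and 7-56% at R = 0.95. Percent change from baseline, which F.3.4 mentions, would couple the two quantities further and was not modelled.

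**The case against.** The strongest reply is that these are exploratory correlations, that the bias may be trivial, and that a sentence of caution is enough. Part of this stands. At R = 0.97 and c = 1 the rate is 6-7%, and no one can tell from the documents where R lies. Set (c) is a rate and four scans exist, so the slope, with its lower figures, is at least as natural a reading as the two-scan difference. But F.3.5 does not present the correlations as descriptive; it says each tests a hypothesis, and the bias exists for any non-zero error.

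Some stronger readings are tempting and are not supported:

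- A reader might infer that the plan specifies a two-year own-change test, because F.3.5 mentions "the change over two years in plaque lipid composition" while F.3.4 uses "the rate of change of plaque characteristics during the first 3 years". The two-year wording illustrates plaque change against HDL-C change, a pair that is not affected.
- A reader might infer that only the risk-factor association aim (aim 3) is touched. The F.3.3 baseline main effect and the pairs sharing scan error, which fit aim 2(c), go beyond it.
- A reader might infer that baseline against year-1-to-year-3 change should replace the planned test. It shares no scan with baseline, but it discards the first treatment year and so answers a different question. It is better kept as an option.

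**Conclusion.** The point holds as a should-fix matter. For own-change pairs, and for pairs sharing baseline measurement error, r = 0 is the wrong null and the nominal 5% level is not kept. The direction is negative for own-change pairs. The size cannot be judged from the documents: the tabulated rates are illustrations that rest on assumed R and c, n = 180, independent scan errors and no true relation between baseline and change. They refer to the MRI measures and do not carry over to laboratory own-change pairs, whose reliability is also not given.

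A reader might infer that F.3.5 as a whole is unsound, or that the treatment comparison is biased. Neither follows. Plaque-laboratory correlations do not share the error, and randomisation balances baseline error between arms in expectation. Adjusting for baseline in F.3.3 is therefore no problem in itself; only interpreting that coefficient, or using its significance as a trigger, is.

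**What to change.** In F.3.5, state that:

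1. A variable will not be tested against its own change, or against a change sharing its baseline error, with the r = 0 null when change is measured from the baseline assessment.
2. Such correlations will be reported as descriptive and labelled as subject to regression to the mean.
3. The coefficient of a baseline value on its own change will not be interpreted as a biological association, in F.3.5 or F.3.3, and its significance will not decide whether an interaction is tested.

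This costs wording only. The downside is that baseline against own change becomes a descriptive result rather than a formal test.

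An optional sensitivity analysis, using scans already scheduled, is the Spearman correlation of baseline with year-1-to-year-3 change. In simulation with constant error it rejected 4.3-5.6% under the null. With error proportional to plaque level, Spearman rejected 5.0-8.1% and Pearson 11.8-38.6%, which is the reason to name Spearman. Its limits should be stated with it:

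- It says nothing about first-year change. If all change falls in year 1 its power is about 5%.
- Power is low if change is early. For a true correlation of −0.3 with 3-year change at c = 0.25 and R from 0.80 to 0.97, it is 31-86% if change is linear and 15-66% if 60% of it falls in year 1 and 90% by year 2.
- It assumes nearly independent scan errors between years. With a year-to-year error correlation of 0.3 it rejects 5-19%.
- It can still reject because of a floor at zero lipid. In one assumed scenario (40% of patients at zero; mean change of −0.3 baseline SD in the rest, unrelated to level) it rejected 41-97%.
- D.3 says "a region of each carotid artery, covered by both baseline and 2-year scans, will be identified", so the report should say which region the year-1 and year-3 values come from. Redefining that region would be more than a wording change and is not asked for here.

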In this research project we will perform carotid MRI studies in 180 CAD patients with a family history of cardiovascular disease and ApoB ≥ 120 mg/dl (LDL-C levels 100-190 mg/dl). Fifty percent of these subjects will be women. The qualified subjects will be randomized to one of three treatment groups: (1) single therapy - atorvastatin alone; (2) double therapy – atorvastatin plus Niacin (2 g/day); (3) triple therapy – atorvastatin, Niacin plus ezetimibe (10 mg/day). . The treatment target for LDL-C will be ≤ 80 mg/dl for the single and double therapy groups and ≤ 60 mg/dl for the triple therapy group. The HDL-C target for two niacin-treated groups will be 10-12 mg/dl increase. All patients will undergo MRI examination of both carotid arteries annually for three years, a total of 4 examinations. If subjects are enrolled in the trial extension a “late time” scan may be performed at a median time of six years.

Following figure illustrates the study design.

*If subjects are enrolled in the trial extension a “late time” scan may be performed at a median time of six years.

In order to determine if carotid plaque characteristics predict future major cardiovascular events, we will ask the study participants who have completed the original 3-year protocol and carotid MRI examinations to continue on their randomized therapy for up to 11 more years. We will (a) continue to conduct clinical follow-up during the extension to collect cardiovascular events including fatal/non-fatal MI or stroke, hospitalization/revascularization for worsening ischemia, and mortality; (b) determine whether plaque characteristics (lipid content, volume and enhancement) at baseline and its change during therapy are statistically associated with cardiovascular events.

Duration: a mean of 5 years and maximum of 11 years

A.3. Primary Efficacy Parameters:

Primary endpoint: The primary endpoint of this study is carotid plaque lipid composition identified by MRI. The determination of plaque lipid content for each carotid artery will be performed using the automated interactive system. These measurements will be performed from the MRI scans at four time points blinded to time sequence of MRI examinations, patient treatment, lipid levels and clinical course.

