Secondary endpoints: 1) carotid plaque fibrous tissue and calcium compositions, 2) carotid lumen area and wall area by MRI. Again, the measurements of minimum lumen area, maximum outer vessel wall circumference, and plaque fibrous tissue and calcium contents will be performed from the MRI scans at four time points blinded to time sequence of MRI examinations, patient treatment, lipid levels and clinical course.

Cardiovascular events: Any cardiovascular events such as death from any cause, non-fatal myocardial infarction, stroke, and revascularization procedures (PCI or CABG) due to unstable ischemia will be recorded and verified.

A.4. Planned Sample Size: In order to have **180** patients with coronary artery disease or carotid stenosis $\geq 15\%$ by ultrasound to complete the study, up to **240** subjects will be enrolled.

A.5. Operating Sites and Investigators:

- (1) UWMC/HMC Cardiology.
- (2) Yakima Heart Center.
- (3) University of Southern California.

The 2 non-UW sites have their local IRB approvals.

B. Study Procedures

B.1. Subject Recruitment:

Potential subjects with coronary artery disease and/or carotid artery disease will be selected from UWMC Cath lab with [name] as the primary subject contact cardiologist. [name] is the principal investigator and contact cardiologist for HMC and NW hospital recruitment. [name] will act as the primary subject contact cardiologist from the Yakima Heart Center. [name] will act as the primary contact cardiologist from University of Southern California.

Subjects will be selected based the following inclusion and exclusion criteria. An initial contact letter will be sent out to the potential subjects by the above-mentioned physicians, co-investigators for this study, at each site. In this initial contact letter, the research program is introduced and further study contact information is provided for subjects to consider. Individuals who are interested in the research program will contact the study coordinators or the investigators for more information and possibly for a screening visit.

B.2. Inclusion and Exclusion Criteria:

Inclusion Criteria

1. Men 67 years of age or younger; women 70 years of age or younger.
2. Family history of cardiovascular disease.
3. At least one 50% stenosis or three 30% coronary lesions post MI, PCI or CABG. Or carotid stenosis >15%.
4. A confirmed fasting ApoB \geq 120 mg/dL.
5. Willing to participate in the study and sign an informed consent form.

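### F.3.5 correlates plaque change with laboratory change apparently across all three arms and names no treatment term, so if plaque change differs by arm a pooled correlation can arise with no association within any arm

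*Combined protocol and SAP*

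**What the plan says.** F.3, item 5 defines four sets of variables: (a) baseline plaque, (b) baseline laboratory values, (c) rate of change of plaque, (d) rate of change of laboratory values. It correlates pairs drawn from different sets. Its leading example pairs a variable from (c) with one from (d): "the change over two years in plaque lipid composition vs. the corresponding change in HDL-C concentration". It says that a change-versus-change correlation tests whether the two items rise or fall together.

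The section does not use the word pooled. Its power statement, however, begins "With our sample size of at least 180 patients who have complete data for up to 3 years" and claims the study is "very likely to detect a true correlation of $r = \pm 0.18$ or larger between variables of interest". Under A.4, 180 is the number of completers for the whole trial. No within-arm or arm-stratified correlation is described. Multivariable expansion is mentioned as an option; the example given is baseline HDL-C with baseline plaque lipid, and treatment is not named.

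A.2 states: "The qualified subjects will be randomized to one of three treatment groups". It then sets targets that differ by arm. For HDL-C, "The HDL-C target for two niacin-treated groups will be 10-12 mg/dl increase"; single therapy has no HDL-C target. The LDL-C target is 60 mg/dl or below for triple therapy and 80 mg/dl or below for the other two arms. Aim 4 in A.1 compares plaque change between arms.

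**The concern.** Randomised arm can influence both members of a change-versus-change pair. The design aims to separate the arms on HDL-C and LDL-C. Whether they also separate on plaque change is what Aim 4 sets out to learn. If they do, patients in the niacin arms will tend to have both a larger HDL-C rise and a different plaque change. A correlation over all patients then picks up the difference between arm means, even if HDL-C change says nothing about plaque change among patients on the same therapy.

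Aim 3 is meant to show which laboratory changes relate to plaque change. A pooled coefficient cannot separate an HDL-C association from any other effect of the assigned drugs. The problem is greatest when treatment works, which is the result the trial hopes for. In the opposite case, where arms differ on HDL-C but not on plaque, the extra HDL-C spread weakens a real within-arm association.

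**Working it through.** **The plan's own figure.** Fisher z for r = 0.18, two-sided 5%, 80% power: N = ((1.960 + 0.842)/atanh 0.18)² + 3 = (2.802/0.1820)² + 3 = 240. At N = 180, power is Φ(0.1820 × √177 − 1.960) = Φ(0.461) = 67.8%, and the smallest r with 80% power is 0.208. The stated figure does not reproduce at 180. It matches 240, the enrolment ceiling in A.4. That is a separate matter; the figure matters here because it shows that the analysis set is the three-arm total.

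**Inputs.** From the documents: 180 completers, three arms, and an HDL-C increase of 10-12 mg/dl targeted in two of them. Assumed, because the documents give no values: equal allocation (60 per arm); mean HDL-C change in the niacin arms 10-12 mg/dl above single therapy; within-arm SD of HDL-C change 6-10 mg/dl; plaque change differing by d = 0.2-0.5 within-arm SD between the niacin arms and single therapy.

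**Pooled correlation with zero within-arm correlation.** In within-arm SD units, let h = shift/SD. With arm means (0, h, h) and (0, d, d), the between-arm covariance is (2/9)hd and the between-arm variances are (2/9)h² and (2/9)d². Hence

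|r| = (2/9)hd / √[(1 + (2/9)h²)(1 + (2/9)d²)].

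Example: shift 10, SD 8, d = 0.5 gives 0.139/√(1.347 × 1.056) = 0.12. The 5% cut-off at N = 180 is |r| = 0.146. The chance of significance follows from Fisher z and was checked with 20,000 simulated trials per setting.

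| Shift (mg/dl) | SD (mg/dl) | d (SD) | Pooled r, absolute | Significant, formula | Significant, simulation |
|---|---|---|---|---|---|
| 10 | 8 | 0 | 0.00 | 5.0% | 5.0% |
| 10 | 10 | 0.2 | 0.04 | 8.3% | 7.7% |
| 10 | 8 | 0.3 | 0.07 | 15.7% | 15.6% |
| 10 | 8 | 0.5 | 0.12 | 34.4% | 34.8% |
| 12 | 6 | 0.5 | 0.16 | 56.0% | 56.9% |

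After centring both variables on their arm means (176 degrees of freedom), the simulated rejection rate is 4.8-5.3%.

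For LDL-C, assume the triple arm is 20 mg/dl lower, SD 20-30 mg/dl, and d = 0.5 in that arm only. The same reasoning gives pooled r = 0.07-0.10.

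**Dilution when plaque change does not differ by arm.** A within-arm r of 0.208 becomes 0.208/√(1 + (2/9)h²) when pooled.
- Shift 10, SD 10: 0.208/√1.222 = 0.188, power about 72%.
- Shift 12, SD 6: 0.208/√1.889 = 0.151, power about 53%.

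Both compare with 80% for the undiluted r.

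**Cost of adjustment if HDL-C change drives plaque change.** Let plaque change depend linearly on HDL-C change across and within arms, with the slope set for 80% pooled power. Simulated arm-adjusted power is 72% (shift 10, SD 10), 68% (10, 8), 63% (12, 8) and 53% (12, 6). The lost degrees of freedom alone would move the detectable r only from 0.208 to 0.209. The rest of the loss comes from removing the randomised part of the HDL-C variation.

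**The case against.** The strongest reply is that the pooled correlation answers a legitimate question. If niacin raises HDL-C and thereby reduces plaque lipid, the two do move together across the trial population. Aim 4 itself treats single versus double therapy as the HDL-raising contrast. Calling a pooled result false presumes a within-arm question that the plan never states, and adjusting for arm discards part of a real signal. This stands, and it is why the pooled coefficient should not be removed. It does not remove the need to say which question each coefficient answers.

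The magnitude also rests on assumptions. The HDL-C target is a rise from baseline, as the dosage adjustment table in C.3 confirms, not a difference from single therapy; the calculation takes mean HDL-C change on atorvastatin alone to be zero. The SDs and plaque differences are assumed, and the upper figure is the extreme corner of the grid.

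Therapy does enter F.3.2, as a candidate predictor of plaque lipid change, and F.3.3, as treatment group. Neither puts arm into the laboratory correlations. The covariates in the F.3.5 example are baseline values, which do not remove a difference that arises after randomisation.

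Three stronger readings are tempting and not supported:
- A reader might infer that the design itself creates spurious correlations. Only the laboratory targets are set by design; a plaque difference is a hypothesis, and without one the pooled error rate is 5%.
- A reader might extend the point to baseline-versus-change pairs. Randomisation (B.5) makes baseline values independent of arm, so this mechanism does not operate there.
- A reader might ask for the F.3.4 Cox models to be stratified by arm, since that section says "These models will use not only the MRI variables but currently identified risk factors as well, such as age and gender" and does not name arm. Its stated question is whether plaque variables add prediction beyond known risk factors. Stratification there is a preference, and nothing calculated here bears on it.

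**Conclusion.** The point holds for pairs that set a plaque change against a laboratory change. Pooling is an inference from the sample size and the absence of any arm term; it is not stated text, but it is the natural reading. Under the assumed ranges, the pooled test is significant in about 8-57% of trials with no within-arm association, against about 5% after adjustment. If plaque change does not differ by arm, false positives stay at 5%, and a within-arm association with 80% power undiluted has about 53-72% when pooled. The direction of the problem does not depend on the assumed values; its size does. It concerns the association analyses of Aim 3, not the primary endpoint comparison.

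**What to change.** In F.3.5, for pairs formed from set (c) with set (d) only:

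1. Prespecify a partial correlation, or the equivalent regression, adjusted for randomised arm with two indicators. For Spearman, apply it to ranks.
2. Report it beside the pooled correlation, and label the pooled one as including the between-arm treatment effect.
3. Base any statement that a laboratory change tracks plaque change independently of assigned therapy on the adjusted result.

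The change needs SAP wording and two degrees of freedom, with no new data. The real cost is power if the laboratory change mediates the treatment effect: about 53-72% for the adjusted test where the pooled test has 80%, under the assumed ranges. Reporting both keeps that information. Baseline-versus-change pairs and the F.3.4 Cox models need no change on this ground.

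### The plan's only power figure is overstated: 180 subjects with complete data give 68% power, not 80%, to detect r = 0.18

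*Combined protocol and SAP*

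**What the plan says.** Section F.3, item 5, covers correlations between pairs of variables drawn from four sets: baseline plaque measures, baseline laboratory measures, and the rates of change of each. The method is given as "The simplest form of these analyses will be the Pearson or Spearman correlation (and scatterplots) between pairs of variables".

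The item closes with a statement of sensitivity: "With our sample size of at least 180 patients who have complete data for up to 3 years we will be very likely to detect". The effect size it names is "a true correlation of $r = \pm 0.18$ or larger between variables of interest". The next sentence fixes the terms: "We are assuming 80% power, 2-sided test", with a significance level of 0.05.

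The number 180 comes from section A.4 (Planned Sample Size). The plan is to have 180 patients "to complete the study, up to 240 subjects will be enrolled". Section A.4 gives no effect size, standard deviation or power. The sentence in F.3 is therefore the only power figure in the document.

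**The concern.** The sentence supplies all four quantities that define the power of a correlation test: sample size, effect size, significance level with sidedness, and power. Any three determine the fourth, so the statement can be checked without outside information. It fails the check.

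What is at stake is how non-significant results under Aim 3 are read. The plan introduces the figure to support its claim that fairly weak correlations can be detected, and it treats each pair of variables as a hypothesis of interest. A reader who takes the sentence at face value would allow a one-in-five chance of missing a true correlation of 0.18. The actual chance is close to one in three.

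**Working it through.** **Inputs.** n = 180, r = 0.18, two-sided α = 0.05 and power 80% (all from section F.3, item 5). Up to 240 enrolled (section A.4). Normal quantiles: 1.960 for two-sided 0.05 and 0.8416 for 80% power.

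**Step 1. Try to reproduce the stated 80% at n = 180.**

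Power ≈ Φ(atanh(r) × √(n − 3) − 1.960); the opposite tail is negligible.

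- atanh(0.18) = 0.1820 and √177 = 13.304; their product is 2.421.
- 2.421 − 1.960 = 0.461, and Φ(0.461) = 0.678.

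Power is 67.8%, not 80%. The miss rate is 32.2%, not 20%.

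**Step 2. Find the n that does give 80% at r = 0.18.**

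n = ((1.960 + 0.8416) / 0.1820)² + 3 = 237.0 + 3 = 240.0.

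**Step 3. Find the correlation detectable with 80% power at n = 180.**

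r = tanh(2.8016 / √177) = tanh(0.2106) = 0.2075.

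**Step 4. See whether another method rescues the figure.**

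| Method (r = 0.18) | Power at n = 180 | n for 80% power |
|---|---|---|
| Fisher z, two-sided | 67.8% | 240 |
| Fisher z with bias correction, two-sided | 68.0% | 239 |
| Noncentral t, two-sided | 68.5% | 237 or fewer |
| Simulation, bivariate normal, 200,000 samples, two-sided | 68.0% | about 240 (80.2% at 240) |
| Spearman, two-sided, variance factor 1.06 assumed | 65.2% | not computed |
| Fisher z, one-sided 0.05 | 78.1% | 190 |

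The two-sided results lie 11 to 15 percentage points below the stated 80%, which is too far to be rounding. A one-sided 0.05 test comes close, but the plan specifies a two-sided test.

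**Step 5. Allow for more than 180 completers.** Two-sided Fisher z power is 72.4% at n = 200, about 76% at n = 220, and 80.0% only at n = 240.

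**The case against.** Four points can be made for the plan.

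- **The sentence gives 180 as a minimum.** More subjects could complete, and pairs made up only of baseline variables do not need three-year follow-up. This is a fair limit on scope: if 240 subjects had baseline data, a baseline-to-baseline correlation of 0.18 would have 80% power. It does not rescue the sentence, which ties its claim to 180 patients with complete data. For correlations involving change, 80% would require complete data from every subject at the enrolment ceiling, whereas section A.4 allows for a loss of 1 − 180/240 = 25%. Section A.1 also speaks of 180 subjects at baseline.
- **The practical difference is small.** Moving from 0.18 to 0.2075 changes the variance explained from 3.2% (0.18²) to 4.3% (0.2075²). Both are weak correlations, so the plan's general claim largely survives. This stands, and it is why the point is a correction and not a threat to the trial.
- **Nothing else depends on the figure.** It does not size the trial and does not bear on the primary plaque-lipid comparison. The plan also has no rule for interpreting null correlations, so a misreading is a risk and not a certainty. This also stands.
- **The origin of the error is unknown.** The required 240 equals the enrolment ceiling, which suggests that the calculation used enrolled subjects and the result was then attributed to completers. The documents do not say so, and a one-sided calculation is another possibility. The discrepancy is the same whatever its source.

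**Conclusion.** The concern holds. The stated power does not follow from the stated inputs. With 180 subjects with complete data, power for r = 0.18 is about 68%, a shortfall of 12 percentage points. The stated 80% belongs to n = 240 or, at n = 180, to a correlation of about 0.21.

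This rests on a single unadjusted Pearson correlation, approximate bivariate normality, and independent subjects. Spearman correlation, which the plan also allows, lowers the power at r = 0.18 to about 65%. The error is confined to the analyses in section F.3, item 5, and bears mainly on correlations that involve change over time. It should be corrected because it is the document's only statement of what the trial can detect.

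**What to change.** Replace the closing statement of section F.3, item 5, with wording such as: *With 180 subjects with complete data, a two-sided 0.05 test of a single Pearson correlation has 80% power for |r| of about 0.21 or more, and about 68% power for |r| = 0.18.*

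If Spearman correlation is to be used, add that power at 0.18 is then about 65%. The detectable value still rounds to 0.21: tanh(0.2106 × √1.06) = tanh(0.2168) = 0.213, under the assumed variance factor of 1.06. If some baseline-only pairs will draw on more than 180 subjects, give their n and power separately.

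The cost is one sentence and a slightly less favourable figure. No patients, procedures, endpoints or tests change. The correction is still useful after data collection, because null correlations will be reported against this benchmark.
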